### **Data Management, Entry, and Storage**

**Overview.** All data will be collected during in-person interviews in private offices at the Acute Psychiatric Inpatient Unit at the Syracuse VAMC, by phone in a private office at Canandaigua VAMC, or chart reviews that take place in either the Syracuse or Canandaigua

VAMC. The Research Compliance Officer for Canandaigua VAMC will be called when patients are consented and given participants' last name and last four digits of their social security number. Other copies of the consent will be delivered in person or through secure VA mail to the Syracuse Institutional Review Board and Syracuse VAMC Medical Records. Only research staff associated with the study will handle or have access to any of the research data collected for this study. Individuals with access to the data will be persons listed on the IRB-approved study protocol. Once paper consent, interview forms, and electronic digital recordings (digital recording machine) are completed, they will be stored in locked file cabinets in a study-dedicated office maintained by the Center for Integrated Healthcare (CIH) located in the D-wing of the Syracuse VAMC, or by the CoE located at the Canandaigua VAMC. All consent forms will be signed by the PI, or co-investigators [name] or [name].

Data from interviews, audio recordings, and chart reviews will be entered into electronic databases from designated offices located at the CIH at the Syracuse VAMC, and the CoE at the Canandaigua VAMC. The study-related research staff or assistants will enter data into a database located in a secure folder on the VISN 2 remote/disconnected "T" drive maintained by the Canandaigua VAMC for use by CoE staff to store all research data. Access to the folder in which the database is located will be restricted to those individuals listed on the IRB-approved study protocol as being associated with this project. Data will be analyzed on the "T" drive as Veteran's Informatics and Computing Infrastructure (VINCI, http://www.hsrd.research.va.gov/for researchers/vinci/), a secure workspace for accessing, storing, and analyzing VA data located on VA secure servers behind VA firewalls will be used to analyze the data. VINCI is funded by HSR&D and is a collaboration between the VA Office of Information Technology (OI&T) and the Veterans Health Administration's Office of Research and Development (VHA ORD). VINCI workspaces are supported by server level redundant backup systems and secured behind extensive VA cyber security systems including VPN secured access, VA authentication systems, encryption and firewall. During the analysis phase data will temporarily be copied to secure storage on the VINCI workspace through a secure file copy. VINCI offers a suite of analytical tools including that will be used to produce the analysis. When the analysis is complete, data stored on the VINCI secure workspace will be returned to the "T" drive. When all data are entered, processed, and analyzed, the paper forms and digital recordings will be maintained and/or destroyed in whatever manner is recommended by the Information Security Officer. De-identified data will be stored indefinitely so it can be used in future publications.

Data Collected During the Screening, Baseline, and Follow-up Assessments. To explain in detail, for each participant, there will be three paper packets, a consent file that contains the patient's name, unique participant ID#, other identifying information, and a copy of the consent form, a data file that contains the measures with the unique participant ID# written at the top of each page but no other identifying information that is stored at the Syracuse VAMC, and a second data file from telephone assessments that is stored at the CoE. In this way, sensitive information from the interviews contained in the measures cannot be linked with identifying information unless one has the consent and a data packet.

Data Collected from Audio Recordings. At the beginning of all audio recordings, the investigator will speak the participant's unique ID#, type of session (e.g., MI-SI session #1, one-month follow-up assessment), and the date of the interview. The recording device will be locked in the file cabinet with the paper packets. The recorded information will be copied to a secure server on a password and firewall protected computer and then the data on the recorder will be erased. The recorded data will remain on the server until it is coded and will be erased

according to VA guidelines. Data from coded MI-SI sessions will also be recorded on paper score sheets that will be stored in the participant's packet with the other measures.

Access to Data. Only the research staff collecting data at Syracuse (not staff or patients at the Syracuse VAMC), research staff responsible for coding, entering and analyzing data, along with [name] will have access to the keys to the cabinets and the password protected computer where data are stored. We will not transmit or share data outside of the VA.

Data Management. Interviewers will visually review all forms for completeness while the participant is in the interview. He or she will discuss any incomplete sections with the participant and encourage completion of the form. Specific forms corresponding to each of the assessment areas (aggression, etc.) will be developed and each page will contain the participant's unique ID# in case pages become detached. A check sheet detailing what needs to be collected during each interview will be kept to ensure data quality. Also, a master check sheet will be developed with a form for each participant to ensure that all procedural requirements (e.g., Consent signed by PI, IRB and Research Compliance Officer notified of new participant, CPRS note entered) are accomplished for each participant.

Data Entry. Once all forms are complete, the interviewer will have his/her packet edited by another member of the study team, and will then enter the data. The system will have appropriate logical and data entry checks built into it to reduce the most common types of data entry errors. The study database will be held on a password protected hard drive that will be backed up weekly. [name] will define the requirements of the system and maintain or refine the system as needed. Once all information is entered and verified, then the original paper records will be returned to their locked cabinets. [name] will review the data each month in order to identify any logical inconsistencies or omissions that may have occurred. Any problems will be brought to the attention of the programmer for remediation. All identifying information will be destroyed in consultation with the Information Security Officer (ISO) in agreement with VA policy.

#### Compensation

Research staff will collect participant's names, social security numbers, and the addresses they wish their reimbursement check be sent to. The information will be shared with CoE support staff, who will instruct accounting to issue a check in the patient's name to be sent to the desired address. Checks will be issued after the patients are discharged from the unit, and after follow-up assessment. Participants who complete the screen will be compensated with a \$10 personal check that will be sent to the address of their choice. Patients who meet eligibility criteria and continue through phase 2 and 3 will receive an \$80 check for completing each follow-up assessment. Participants who are discharged prior to completing both MI-SI sessions will still be eligible for the follow-up appointment. An \$80 remuneration for the follow-up is required to compensate subjects for any expense they have to make the interview, time for the assessment, and as encouragement to maintain contact with the researchers. This level of remuneration is consistent with the minimum recommended amount for retaining subjects in substance abuse treatment research, does not promote substance abuse and is not perceived as coercive by participants . By completing the screen (\$10), and the 3 follow-up assessments (\$240), participants can earn \$250.

## **Human Subjects**

### Risk to Subjects

**Human Participants Involvement and Characteristics.** All participants will be at high risk for emerging suicidality, suicidal behavior, and other negative outcomes. Suicidal behavior is also an outcome and is therefore expected to occur. Safeguards will be built into the study to prevent suicidal behavior before it occurs, and to ensure an appropriate response.

**Potential Risks.** There are no physical risks in this study. Psychological risks are 1) emerging suicidality, 2) distress caused by the personal nature of the interview, recalling distressing events and life problems, and discussing suicide-related issues, and 3) potential need to break confidentiality in the event of suicide risk or violence risk or child abuse.

### **Protection from Risk**

**Suicidality.** Participation in the study will provide patients who are at elevated risk for emerging suicidality, suicidal behavior, and other negative outcomes with a formal assessment of suicide risk on the unit and a re-assessment of risk one, three and six months after discharge. Participating in the study will provide more information on patients' suicide risk than would otherwise be available. If the interviewer becomes aware that a participant might be thinking about or planning to make an attempt, the interviewer will ask the following questions: 1) Do you have a desire to kill yourself that you think you might act on? 2) Do you have a plan for killing yourself?, and 3) Do you intend to carry the plan out? After the interviewer has noted any suicide desire, plans, or intent, the interviewer will review available assessment measures that may help evaluate the severity of the participant's risk. If the interviewer determines the participant is at imminent risk, the appropriate safety plan will be initiated.

Inpatient Safety Plan. Baseline and MI-SI interviews will take place while participants are on the unit, ensuring 24-hour availability of hospital staff and emergency services. If patients are determined to be at imminent risk for suicide, the interviewer will inform clinical staff of the participant's risk so that staff can attend to their needs. All participants will be informed that interviewers will need to disclose participants' risk level to clinical staff during the informed consent process. To aid in the protection and treatment of participants, interviewers will always inform participants of their desire to inform clinical staff. If a decision is made to notify staff, the interviewer will speak with a member of the treatment staff responsible for clinical care by phone or in person. The persons to contact will be clarified with program administrators prior to implementing the study, and information that bears directly on risk (e.g., level of depression, suicide plan, access to a weapon, prior attempts, etc.) will be disclosed. If clinical staff desires, interviewers will serve as a resource to treatment staff, providing guidance and consultation in developing a safety plan. All clinical decisions will be made by the Syracuse VA clinical staff, and interviewers will in no way usurp their authority.

To protect participants who are involuntarily hospitalized to ensure that they realize that their participation in the study is voluntary, researchers will have a staff member witness the informed consent process (please note that there is a witness signature line on the consent form).

Telephone Safety Plan. Participants who are randomized to the Motivational Interviewing to Address Suicidal Ideation (MI-SI) condition will receive one telephone MI-SI session after discharge and all follow-up assessments will be conducted by telephone. Emergency procedures will be initiated if patients are determined to be at imminent risk for suicide using the risk assessment described above. Participants determined to be at risk will be asked if they are

willing to be transferred to the Veteran Crisis Line. Veteran Crisis Line responders are well trained in emergency procedures and have working protocols for locating callers and initiating rescues. All telephone sessions will be conducted at the Center of Excellence (CoE) to ensure that the clinicians' telephone is set up for transfers to the Crisis Line. Calls can be transferred with a four step process.

#### Warm Transfer Process

- 1. Press the **conference** button.
- 2. Dial [name] press option 1 and a Crisis Line responder will answer.
- 3. Describe the participants risk and provide name and telephone number.
- 4. Pressing the **conference** button and participants will be linked with Crisis Line counselors.

It is possible that participants may refuse to be transferred to the Crisis Line or hang up. As a result, research clinicians will ask participants to use a landline for MI-SI telephone sessions so that the number can be tracked to an address if emergency services are needed. For participants who only have a cell phone, interviewers will begin each session by asking the participant for the address from which they are calling so that the clinician can send help if it is needed. Because participants may give a false address, clinicians will consult with Crisis Line responders who have a protocol for emergency responses for cell phone callers.

Adverse Events (AE). All suicide attempts and episodes of imminent risk that require intervention will be considered adverse events and will be addressed according to IRB regulations. The determination of an AE will be made by an investigator other than the PI (i.e., [name] or [name]), to reduce the possibility of bias. Syracuse VA IRB also requires that serious adverse events, any event leading to a deviation from the protocol such as emergency hospitalization (e.g., to address acute suicidality) or death, be reported to the principal investigator within 24 hours, who is required to report them to the IRB within 48 hours. Adverse events that are minor such as temporary distress will be recorded by interviewers and reported to the IRB annually. All adverse events will be reported to the principal investigator within 24 hours to establish the level of significance and determine the appropriate procedure.

**Distress.** If, during any interview, participants appear to be disturbed by the content of the interview, the interviewer will stop asking questions and provide support, and if distress persists, suspend the interview. If distress is experienced by participants on the unit, interviewers will disclose the participants' distress to treatment providers so that staff may follow up with the participant therapeutically and monitor their condition, with the participants' permission. In the rare event that distress is severe such that there is immediate danger to the participant or to others, staff will be informed immediately. Participants, however, will be informed of the interviewer's decision. Discomfort may also arise later that day. Participants will be informed this may occur and will be encouraged to speak with a staff member, the interviewer, or another investigator involved in the study. If participants become distressed during the follow-up interview, interviewers will discuss scheduling an appointment at a local facility during the follow-up assessment session to increase the chance that the participant will engage in treatment, and provide the phone number of the National Veterans Crisis Line ([name]).

**Confidentiality**. During the informed consent process, participants will be informed of the limits of confidentiality which include the need to break confidentiality if the participant is determined to be a threat to self or others and if a child is exposed to abuse or neglect. The assessment battery does not contain questions about planned acts of violence or questions about abuse or

neglect of children, other than the suicide risk assessments. If participants spontaneously report plans or intent to carry out an act of violence, or spontaneously disclose child maltreatment, the interviewer will contact the primary investigator to make a plan that may include, depending on the nature of the information, a disclosure to treatment staff and making a child abuse report.

To add a further layer of protection for our participants we will apply for a Certificate of Confidentiality from the National Institute of Mental Health (NIMH). Confidentiality Certificates are issued by the National Institutes of Health (NIH) pursuant to Section 301 (d) of the Public Health Services Act (42 U.S.C. Section 241(d)) to afford special privacy protection to research participants. A Certificate helps the researcher avoid compelled "involuntary disclosure" (e.g. subpoenas) of identifying information about a research participant. It does not prevent voluntary disclosures such as disclosure to protect the subject or others from serious harm, as in cases of child abuse. Also, a researcher may not rely on a Certificate to withhold data if the participant consents to the disclosure. NIMH requires a letter of approval from the IRB prior to awarding a Certificate of Confidentiality to an investigator. Certificates of Confidentiality were successfully obtained for the two pilot studies we conducted on the Acute Inpatient Unit at the Syracuse VAMC.

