## **Specific Aims**

Psychiatrically hospitalized Veterans are estimated to be at 40-50 times the risk for suicide than the general population in the year following discharge.  Despite their elevated risk, there are no clinical studies testing suicide interventions that are tailored to the population. To initiate a program of research that will address this need, we will conduct a randomized controlled trial (RCT) to examine the efficacy of Motivational Interviewing to Address Suicidal Ideation (MI-SI) plus TAU on suicidal ideation (SI) when compared to TAU alone. The study will include 140 high-risk Veterans who are hospitalized on a VA psychiatric inpatient unit. "High-risk" will be defined as scores over 2 on the Beck Scale for Suicidal Ideation (SSI), which prospectively predicts suicide. 

All participants will receive a baseline assessment of SI, suicidal behavior, and risk factors for suicide. Half will be randomized to MI-SI plus TAU and half to TAU alone. Participants in the MI-SI group will receive two sessions of MI-SI during their hospitalization plus one MI-SI telephone booster session in the month following discharge, in addition to TAU. All participants will be asked to complete telephone follow-up assessments at 1, 3 and 6 months after discharge. The primary outcome is change in the severity of SI. In exploratory analyses we will also examine the impact of MI-SI on treatment engagement, and treatment engagement as a mediator of the impact of MI-SI on change in the severity of SI.

The impact of the intervention on suicide risk during hospitalization is also of critical importance. In exploratory analyses, we will examine the effect of MI-SI on the severity of SI during the inpatient stay. Additionally, MI has been found to impact clients' in-session talk about making changes, which is associated with treatment outcome. In participants who receive MI-SI, we will examine the impact of in-session living talk (or talk associated with interest in living) and suicide talk (or talk associated with interest in suicide) on the severity of SI during hospitalization.

**Aim 1:** To conduct a randomized controlled trial (RCT) of 140 participants who are at high-risk for suicide. Participants will be randomized to receive MI-SI plus TAU, or TAU alone.

**Aim 2:** To evaluate whether MI-SI plus TAU results in significant reductions in suicidal ideation (SI) and increases in treatment engagement when compared to TAU alone.

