**CPRS Notes.** After the informed consent process is completed, researchers will enter a Study Initiation Note into the participants' digital medical record. To ensure that mental health staff is aware of patients' participation, the attending psychiatrist and nurse manager of the unit will be added as a signees. They will also be added to MI-SI session noted which will document whether the individual exhibited suicidal ideation, plan, or intent during the session.

Participant Procedures. The study will consist of three phases. Phase 1, the assessment phase (15 min.), will be conducted on day 2 or 3 of hospitalization to confirm eligibility. Eligible participants will immediately complete the baseline assessment of risk factors and outcome variables (50 min.). Phase 2, the treatment phase, will occur between day 2 or 3 and discharge. Participants will be randomized to MI-SI plus TAU or to TAU alone. The MI-SI plus TAU condition will include one or two sessions of MI-SI (50 mins. each) in addition to TAU. Sessions will be held on consecutive days and recorded using a digital audio recorder, which will be coded for clinician fidelity. Phase 3, the follow-up phase, will take place after discharge. Participants in the MI-SI plus TAU condition will complete 1 booster MI-SI telephone session within 1 month of discharge (30-50 min.). All participants will be contacted by telephone to complete follow-up assessments (50 min.) at 1, 3, and 6 months to measure outcome variables and risk factors. Research assistants who are blind to condition will complete follow-up assessments.

Table 3: Complete List of Measures

			Time of Assessment			
Domain	Measure	Purpose	Screen	Baseline	*Follow-ups	**Follow- ups after discharge
Demographics	UAB	Screen				
Veteran Status	UAB	Screen				
Psychotic Disorders	MINI	Screen				
Manic Episode	MINI	Screen				
Cognitive Deficits	MMSE	Screen				
ТВІ	TBI-ID	Screen				
Suicidal Ideation (SI)	SSI	Outcome				
Depression	PHQ-9	Risk Factor				
PTSD	PCL-C	Risk Factor		$\sqrt{}$		
Anxiety	BAI	Risk Factor		$\sqrt{}$		$\sqrt{}$
Alcohol Use	AUDIT	Risk Factor		$\sqrt{}$		$\sqrt{}$
Drug Use	DAST-10	Risk Factor		$\sqrt{}$		
Substance Use	SUF	Risk Factor		$\sqrt{}$		$\checkmark$
Frequency						
Substance Problems	InDUC	Risk Factor		V		V
Insomnia	ISI	Risk Factor		V		$\sqrt{}$
Anger	LHA	Risk Factor		V		
Suicidal Behavior	C-CSSRS	Risk Factor		V		V
Contemplation Ladders	CL	Risk Factor		√	$\sqrt{}$	$\sqrt{}$
Treatment Engagement	TSR	Outcome		√		$\sqrt{}$

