**In-Hospital Follow-ups.** These assessments will be conducted 2-3 days and 3-5 days after the baseline assessment, during the course of hospitalization. If patients are discharged during this time, only the first follow-up will be obtained. Participants will be asked to complete a "modified" SI that assesses suicidal ideation over the past 48 hours to assess recent change , Contemplation Ladders and the PDM. When it is time to conduct the in-hospital follow-up assessment, a researcher on the unit will call a researcher at the CoE who will conduct the assessment by telephone. This will ensure that outcome assessments are conducted by researchers who are blind to condition.

**Post-Discharge Follow-ups.** Follow-up assessments will be conducted at 1, 3, and 6 months via telephone. A telephone follow-up will enable us to expand the catchment area and assess

participants who are hospitalized or in residential treatment and unable to return to the medical center. Procedures will include mailing participants the assessment measures to ease administration. There is precedence for this strategy, as the telephone administered SSI was the primary outcome for the PROSPECT trial, supporting use of the method.  In addition to the SSI, we will also use all risk-factors measures that are used at baseline including the PHQ-9, PCL-C, BAI, AUDIT, DAST-10, SUF, InDUC, ISI, C-SSRS, Contemplation Ladders, HCCQ, TSRQ, PCQ, PDM as well as the exploratory outcome measure the TSR-6 (Table 3). The window for each assessment will open at the midpoint between the previous assessment and the current assessment, and close at the midpoint between the current assessment and the following assessment (e.g., open two weeks before month 1 and close at the end of month 2, the midpoint between 1 and 3 month assessments), and close 3 months after the 6-month follow-up.

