Power Analysis: Recruitment will provide data on 112 participants. Assuming a retention rate of 80%, data on 90 participants will be available at the 6 month follow-up. To estimate the statistical power afforded by 90 participants for the severity of SSI, power analyses were conducted using STATA 11 101 "sampsi2" package, which uses calculations based on Frison and Pocock model. 102 Specifying method of analysis (change), number of baseline assessments (1), number of post assessments (3), correlation between baseline and follow-up scores (r = .50), correlation between follow-up scores (r = .70), and standard deviation (sd = 8.4) for the outcome variable using Frison and Pocock's recommendations and our pilot data. we would have .94 power to identify a 5-point difference in mean SSI scores between treatment arms, .81 power to identify a 4-point difference, and .60 power to identify a 3-point difference. The study would therefore be adequately powered to find an effect size of .5 for the primary outcome. If there is concern that the experimental intervention caused harm and the trial is not stopped, we will conduct two-sided analyses instead of the one-sided analyses we proposed. Power analyses suggest we will have .88 power to identify a 5-point difference, .71 power for a 4-point difference, and .47 power for a 3-point difference with the proposed 90 participants (45 in each group), indicating that the trial will still be fairly well powered.

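### Imminent-risk episodes and minor distress can be detected at two or three extra contacts in the MI-SI arm only, and no source of detection is recorded, so adverse-event counts are expected to lean against MI-SI

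*Combined protocol and SAP*

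**What the plan says.** **What becomes an adverse event.** Under Adverse Events (AE), "All suicide attempts and episodes of imminent risk that require intervention will be considered adverse events". The definition does not depend on which contact brings the episode to light. Minor events such as passing distress are recorded by interviewers and reported to the IRB annually.

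**Contacts common to both arms after randomization.** On the in-hospital follow-ups: "These assessments will be conducted 2-3 days and 3-5 days after the baseline assessment, during the course of hospitalization", with the proviso "If patients are discharged during this time, only the first follow-up will be obtained". Telephone assessments follow at 1, 3 and 6 months. That makes five, or four after an early discharge.

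**Contacts in the MI-SI arm only.** Specific Aims gives "two sessions of MI-SI during their hospitalization plus one MI-SI telephone booster session in the month following discharge". Participant Procedures says instead: "The MI-SI plus TAU condition will include one or two sessions of MI-SI (50 mins. each) in addition to TAU", and also provides for the booster. The excess is thus two or three contacts when the booster is held. The two statements on the number of inpatient sessions need to be reconciled.

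**Those contacts are detection points.** CPRS Notes refers to an "MI-SI session noted which will document whether the individual exhibited suicidal ideation, plan, or intent during the session". The Inpatient Safety Plan names the MI-SI interviews. The Telephone Safety Plan says that MI-SI participants "will receive one telephone MI-SI session after discharge and all follow-up assessments will be conducted by telephone", and applies the same emergency procedures to both kinds of call.

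**What a worry about harm can lead to.** The Power Analysis section reads: "If there is concern that the experimental intervention caused harm and the trial is not stopped", in which case the tests become two-sided. The Data Monitoring Committee receives serious adverse events as they occur and may recommend probation or termination.

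**The concern.** With equal true risk, the arm with more conversations about suicide offers more occasions on which an episode can be noticed. Nothing in the plan records where an event was found, and nothing provides a like-for-like count. A reader of the totals could not tell more risk from more observation.

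This matters because the plan lets a worry about harm change the primary test or precede stopping, without saying what evidence would count. An emergency hospitalization for acute suicidality is one of the protocol's examples of a serious adverse event. A booster call that led to one would therefore reach the committee through a contact with no counterpart in the TAU arm. The lack of a source field also works in the other direction: a true excess on MI-SI would be easy to dismiss as better detection.

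**Working it through.** **1. The plan's own figures.** The documents give no adverse-event rate. The only stated figures that a harm signal would touch are the power values.
- Inputs (Power Analysis): 45 per arm, SD 8.4, correlations .50 (baseline to follow-up) and .70 (between follow-ups), one baseline and three follow-up assessments.
- Frison-Pocock change-score factor: (1 + 2 × .70)/3 + 1 − 2 × .50 = .80.
- Effective SD = 8.4 × √.80 = 7.51. Standard error = 7.51 × √(2/45) = 1.584.
- For a 4-point difference, 4/1.584 = 2.525. One-sided power = Φ(2.525 − 1.645) = .811. Two-sided power = Φ(2.525 − 1.960) = .714.

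The plan states .81 and .71. Its values for 5 and 3 points also reproduce to within .01. A switch to two-sided testing therefore costs about .10 of power at 4 points.

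**2. Contacts.** TAU has 2 + 3 = 5. MI-SI has 5 + 2 = 7 or 5 + 3 = 8. The ratios are 7/5 = 1.4 and 8/5 = 1.6.

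**3. Detection model.** Equal true risk is assumed. Each contact independently yields a recorded event with probability q. The value of q is an assumption, shown from .01 to .10. There are 112/2 = 56 participants per arm.
- Expected events = 56 × k × q, where k is the number of contacts.
- False signal = the probability that a one-sided conditional binomial test of two Poisson counts gives p ≤ .05 against MI-SI.

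| q | Expected events, k = 5 / 7 / 8 | False signal, 5 v 5 | 6 v 5 | 7 v 5 | 8 v 5 |
|---|---|---|---|---|---|
| .01 | 2.8 / 3.9 / 4.5 | .014 | .027 | .045 | .070 |
| .02 | 5.6 / 7.8 / 9.0 | .025 | .053 | .096 | .155 |
| .05 | 14.0 / 19.6 / 22.4 | .035 | .096 | .202 | .345 |
| .10 | 28.0 / 39.2 / 44.8 | .038 | .145 | .345 | .585 |

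The 6 v 5 column stands for overlap that leaves one effective extra contact, which is also an assumption.

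**4. Counting participants instead of events.** The probability of at least one recorded event is 1 − (1 − q)^k. At q = .05 it is 1 − .95^5 = 22.6% on TAU, against 30.2% (k = 7) or 33.7% (k = 8) on MI-SI. For q = .01, .02, .05 and .10:
- A one-sided Fisher test at .05 falsely signals harm in .044, .093, .173 and .271 of trials at 7 v 5, and in .069, .147, .293 and .461 at 8 v 5. With equal contacts the range is .013 to .034.
- MI-SI has the numerically larger count in .59, .67, .79 and .865 of trials at 7 v 5, and in .66, .76, .89 and .95 at 8 v 5. With equal contacts the range is .41 to .46.

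**5. Effect of the remedy under this model.** Restricting a count to the five common contacts brings the expected ratio to 1.00 and the false-signal probability to the equal-contact values above.

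**The case against.** **No such test is planned.** The Analytical Plan contains no between-arm comparison of adverse events. The Data Monitoring Committee section describes individual reporting of serious events and yearly information on progress, not tallies by arm. The harm clause in Power Analysis is not tied to adverse-event counts. This stands. A reader might infer that the trial's own monitoring would raise a false alarm in about a third of trials, or that biased counts will drive the committee. The documents do not support either inference: the .345 comes from a comparison the plan does not contain, at the maximum number of contacts and an assumed 5% detection rate.

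**Suicidal behavior is already compared evenly.** The plan models C-SSRS behavior over follow-up, gathered in both arms by assessors meant to be blind, and the 6-month chart review covers both arms. This stands for attempts. It does not cover every imminent-risk episode. The follow-up chart review is limited to the six months after discharge, and the baseline review follows the baseline interview, so neither is stated to cover the rest of the inpatient stay.

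**The contacts are not independent.** Inpatient sessions fall close to assessments that look back 48 hours, on a unit staffed around the clock. The booster, placed in weeks 3-6 in one description, falls inside the 1-month assessment window. One episode could be found at either kind of contact. This stands and reduces the size: see the 6 v 5 column. Not everyone has the maximum either; in pilot study #1, 9 of the 13 treated participants completed two sessions.

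**Restricting the evidence could hide harm.** A reader might conclude that arm comparisons should use only commonly ascertained events. That goes too far, because it would drop episodes that a session itself provoked. This stands, and it shapes the fix.

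Determination of adverse events by an investigator other than the PI does not answer the point. It governs judgement rather than detection, and is not stated to be blind to arm.

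**Conclusion.** The point holds for imminent-risk episodes and minor distress. MI-SI participants have two or three more contacts at which these can be found, so recorded counts are expected to lean against MI-SI when true risk is equal. The direction follows from the schedule; the size is unknown. With 56 per arm, independent contacts and 1-10% detection per contact, an unplanned one-sided raw-count comparison would mislead in about 5-35% of trials with two extra contacts and 7-59% with three. With one effective extra contact the range is about 3-15%. The detection rates, the independence of contacts and equal sensitivity of a therapy session and a structured interview are all assumptions. Even where a formal imbalance is unlikely, a numerical excess is more likely than not, and the harm clause sets no threshold. If it led to two-sided testing, power at 4 points would move from .81 to .71. This is a cheap improvement in how harm is read, not a flaw in the primary analysis.

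**What to change.** In the Adverse Events paragraph, add a source-of-detection field to the record, completed when the event is logged: common assessment, chart review, MI-SI session, or other. Report adverse events by arm in two ways: in total, and restricted to sources common to both arms. Show MI-SI-session detections separately. State in Power Analysis and in the Data Monitoring Committee section that anyone judging a concern about harm, or advising on continuation, sees both tables. No event is excluded from harm monitoring, and the handling and reporting of each event stay as they are.

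The cost is one form field and one extra table. Session notes and recordings would allow some sources to be reconstructed later, but prospective recording is more reliable. The drawback is that the common-source count omits real events seen only in an MI-SI session, so it must stand beside the full count and never in its place.
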